1.2 Study objectives and endpoints

Table 1-2 Objectives and related endpoints

Objective	Related endpoint and Definition	Analysis method
Primary objective		

Objective	Related endpoint and Definition	Analysis method

To demonstrate that LCZ696 is superior to ramipril in delaying the time-to-first occurrence of the composite endpoint of CV death, HF hospitalization or outpatient HF in patients with LV systolic dysfunction and/or pulmonary congestion following an AMI
	
The primary efficacy endpoint is defined as the time to the first confirmed occurrence of CV death, heart failure hospitalization* or outpatient heart failure**.
 
* Heart failure hospitalization also includes the development of new symptomatic heart failure during an ongoing hospitalization including the index AMI hospitalization.
 
** Outpatient heart failure is defined as:
 
 • An urgent/unscheduled visit to an ED, acute/urgent care facility or outpatient clinic or a non-urgent office/practice or study visit for a primary diagnosis of HF that does not require an overnight hospital stay. • Patients must exhibit at least one documented new HF symptom with objective evidence of clinical HF consisting of at least 2 physical examination findings or one physical examination findings and at least one laboratory criterion. • The event requires initiation or intensification of treatment specifically for HF. Such treatment can include administration of intravenous agent (e.g., diuretic, vasodilator, vasopressor, or inotrope) or mechanical or circulatory intervention for HF, OR initiation of oral loop diuretic treatment, or intensification of oral maintenance loop diuretics for the diagnosis of HF, over a sustained period (i.e., initiation or doubling of total daily dose through a period of ≥ 4 weeks), which is confirmed at a subsequent outpatient visit 	
Section 2.5

Secondary objective
		

To demonstrate the superiority of LCZ696, compared to ramipril, in delaying the time-to-first occurrence of CV death or HF hospitalization
	
Time-to-first occurrence of CV death or HF hospitalization (days).
	
Section 2.6


To demonstrate the superiority of LCZ696, compared to ramipril, in delaying the time to new onset of symptomatic HF defined as time-to-first occurrence of HF hospitalization or outpatient HF
	
Time-to-first occurrence of HF hospitalization or outpatient HF (days)
	
Section 2.6

To demonstrate the superiority of LCZ696 compared to ramipril, in delaying the time-to-first occurrence of CV death, non-fatal spontaneous MI^{1,3} or non-fatal stroke⁴
	
Time-to-first occurrence of CV death, non-fatal spontaneous MI^{1,3} or non-fatal stroke⁴ (days).
	
Section 2.6

Objective	Related endpoint and Definition	Analysis method
To demonstrate the superiority of LCZ696, compared to ramipril, in reducing the rate of the composite endpoint of CV death and total (first and recurrent) hospitalizations due to HF, non-fatal spontaneous MI ^{1,3} or non-fatal stroke ⁴	Cumulative number of composite endpoint of CV death and total (first and recurrent) hospitalizations due to HF, non-fatal spontaneous MI ^{1,3} or non-fatal stroke ⁴ (count).	Section 2.6
To demonstrate the superiority of LCZ696, compared to ramipril, in delaying the time to all-cause mortality	Time to all-cause mortality (days).	Section 2.6
To evaluate the safety and tolerability of LCZ696 compared to ramipril	
 • Number and percentage of adverse events, serious adverse events, drug-related discontinuations, etc. • Change from baseline in laboratory assessments and vital signs measurements 	Section 2.7
[REDACTED]	[REDACTED]	[REDACTED]
[REDACTED]	[REDACTED]	[REDACTED]
[REDACTED]	[REDACTED]	[REDACTED]
[REDACTED]	[REDACTED]	[REDACTED]
[REDACTED]	[REDACTED]	[REDACTED]
[REDACTED]	[REDACTED]	[REDACTED]

Objective	Related endpoint and Definition	Analysis method
[REDACTED]	[REDACTED]	[REDACTED]
[REDACTED]	[REDACTED]	[REDACTED]
[REDACTED]	[REDACTED]	[REDACTED]
[REDACTED]	[REDACTED]	[REDACTED]
[REDACTED]	[REDACTED]	[REDACTED]
[REDACTED]	[REDACTED]	[REDACTED]

Objective	Related endpoint and Definition	Analysis method
[REDACTED]	[REDACTED]	[REDACTED]
[REDACTED]	[REDACTED]	[REDACTED]
[REDACTED]	[REDACTED]	[REDACTED]
[REDACTED]		
[REDACTED]	[REDACTED]	[REDACTED]
[REDACTED]	[REDACTED]	[REDACTED]
[REDACTED]	[REDACTED]	Section 2.13.1

Objective	Related endpoint and Definition	Analysis method
[REDACTED]	[REDACTED]	[REDACTED]

 1. The protocol-defined spontaneous MI is comprised of CEC adjudicated Type 1 and Type 2 MI. 2. Refers to any hospitalization after discharge from hospitalization due to qualifying MI 3. Non-fatal spontaneous MI is CEC-confirmed Type 1 or Type 2 MI that occurred at least 14 days prior to death. 4. Non-fatal stroke is comprised of all CEC-confirmed stroke. 		

2 Statistical methods

The following section contains important information on detailed statistical methodology used for analysis and reporting purposes.

2.1 Data analysis general information

Data will be analyzed by Novartis Biostatistics and Statistical Reporting department according to the statistical analysis section 9.1 of the study protocol using SAS 9.4, unless otherwise specified. Further details on planned statistical analyses and data-driven regression diagnostics will be presented in the following section and in CSR Appendix 16.1.9. The same analysis plan will also be used for planned interim efficacy analyses, as applicable.

In general, the continuous variables will be summarized descriptively by presenting n, mean, SD, median, quartiles, minimum and maximum while categorical variables will be summarized by presenting count and percentage of patients in each category. Graphical presentation of summary data will also be provided as applicable.

For time-to-event variables, the general censoring methods are specified in Section 2.5.3 for fatal or non-fatal time-to-first event endpoints, and in Section 2.6.1 for time-to-recurrent event endpoints.

Some missing or partially missing dates in the analyses require imputation. The handling of missing or partially missing dates has been detailed in Section 5.1.

The randomization in this study will be stratified by region and type of MI (STEMI or NSTEMI). “Other” type of MI has been grouped together with “NSTEMI” as “NSTEMI/Other” type of MI for stratification at randomization. In this document, “NSTEMI” refers to the grouping of “NSTEMI/Other” for type of MI. The stratification factors will be appropriately accounted for in the planned statistical analyses. At Visit 101 all eligible patients will be randomized via Interactive Response Technology (IRT) to one of the treatment arms. The stratification factors of region and type of MI entered and used by IRT at randomization sometimes can be different from the data collected on the Case Report Form (CRF), which is called mis-stratification. In this study, there have been some cases of mis-stratification by type of MI and one case of mis-stratification by region. Analyses using region and/or type of MI will consider the following rules:

- In general, unless otherwise specified, statistical models for all efficacy endpoints will use region and type of MI based on information from IRT where applicable.
- In addition, the primary/main analysis model for each of the primary and secondary efficacy endpoints (Section 2.5 and 2.6) will be repeated using CRF based region and type of MI.
- Subgroup analyses corresponding to the primary/main analysis models for the primary and secondary efficacy endpoints (Section 2.5 and 2.6) will be repeated using both IRT and CRF based region and type of MI where applicable.
- For patient disposition, demographic and background characteristics data analyses: the subgroup definition of type of MI (Table 2-1) will use both IRT and CRF based information; the subgroup definition of region (Table 2-1) will use CRF based information.
- For exposure and safety data analyses, the subgroup definitions of type of MI and region (Table 2-1) will be based on data collected from CRF.

Two interim analyses (IAs) are planned to assess efficacy. The analysis cutoff date for the first IA will be determined as date when 2/3rd of target primary composite outcome i.e. approximately 472 primary composite outcomes will be reported and adjudication-confirmed. The analysis cut-off time for the second IA (IA2) is planned to be 01-Mar-2020 (estimated start of COVID-19 impact globally). All primary events that occurred prior to 01-Mar-2020, will be included in the second IA. Analyses using pre-Covid data (prior to 1-Mar-2020) will include patients randomized before 1-Mar-2020. It is estimated that the second IA will include approximately 80% of the target number of 708 Clinical Event Committee (CEC)-confirmed primary events. If the assumptions of the study design regarding event rate, accrual rate and drop-out rate remain valid, the final analysis cut-off date will be a predicted date when a total of 708 confirmed primary triple composite and 592 confirmed double composite events have been achieved, or study termination has been decided based on other study termination criteria. The final analysis cut-off date for this study is 31-Dec-2020.

Additional efficacy analyses (for primary, secondary, [REDACTED] efficacy endpoints) will be considered to assess the potential impact of COVID-19 on study outcomes. See the following table for an overview of these analyses under different trial conduct scenarios:

Scenario	Primary/main analysis	Sensitivity/supplementary analysis
Early termination (without IA2)	Pre-specified primary/main analysis model, using pre-Covid data (prior to 1-Mar-2020)	Pre-specified primary/main analysis model, using all data accrued up to the end-of-study analysis cut-off
With IA2, early stop	Pre-specified primary/main analysis model, using pre-Covid data (prior to 1-Mar-2020)	Pre-specified primary/main analysis model, using all data accrued up to the end-of-study analysis cut-off
With IA2, no early stop	Pre-specified primary/main analysis model, using all data accrued up to the end-of-study analysis cut-off (31-Dec-2020)	Pre-specified primary/main analysis model, using pre-Covid data (prior to 1-Mar-2020);

		For primary endpoint, additional sensitivity and supplementary analyses will be performed as specified in Section 2.5.4
Note: Analyses using pre-Covid data (prior to 1-Mar-2020) will include patients randomized before 1-Mar-2020. 		

2.1.1 General definitions

Study treatment or drug

In future sections through this document, ‘study treatment’ or ‘study drug’ will be used to refer to investigational therapy assigned to a patient. Specifically, for the double-blind treatment phase, study treatment refers to LCZ696 or ramipril as assigned to a patient at randomization.

Screening epoch or screening period

Screening epoch or screening period is defined as the period starting from date of signed of informed consent until date of randomization or decision on randomization.

Randomized treatment phase

The randomized treatment phase begins at the time of randomization and ends with the last study drug intake or the death of the patient, whichever comes earlier. During the randomized treatment phase, patients will return for scheduled clinic visits. For all related safety analyses randomized treatment starts with the first intake of randomized, double-blind study drug. Temporary interruption of the study drug will not be counted as randomized treatment phase discontinuation.

Post-treatment follow-up phase

The post-treatment follow-up phase (usually after premature permanent study drug discontinuation) begins after last study drug intake + 1 day and ends on the date last seen (or vital status confirmed by indirect contact).

Double-blind period or double-blind treatment epoch

The double-blind period, also called the double-blind treatment epoch, is the combination of the randomized treatment phase and the post-treatment follow-up phase.

Baseline and study day

For analysis purpose, baseline value for all variables is defined to be the last results obtained at or prior to randomization date (or prior to 1st study drug intake for safety assessments). Most of variables will have their baseline at visit 101, unless otherwise specified. [REDACTED]

Study day of any assessment refers to the number of days to the assessment relative to randomization (day 1), or relative to the 1st study drug intake for safety assessments.

Unscheduled visit

Only for the analysis of safety laboratory evaluation will unscheduled measurements be taken into account. For efficacy evaluations, measurements from unscheduled visits will generally not be used, unless specifically specified.

On-treatment data for an efficacy endpoint

The on-treatment data refers to any observation occurring while the patient is on-study medication or within 28 days inclusive of permanent treatment discontinuation excluding any observation occurring thereafter.

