Patients that cannot tolerate dose level 3 will be allowed to stay at level 1 or 2 as maintenance dose. Study drug dose level adjustments should be based on overall safety and tolerability with special focus on a) symptomatic hypotension, b) any clinically significant decrease in eGFR/increase in creatinine (Cr) and c) hyperkalemia (Table 3-3). Treatment guidelines for blood pressure management and hyperkalemia are provided in Appendix 4 and Appendix 5, respectively. Every attempt should be made to maintain patients on the target study drug dose (dose level 3) or maximally tolerated dose levels throughout the trial. If the patient does not tolerate the target study drug dose level the investigator should consider, if appropriate, adjusting non-disease-modifying background medications (e.g., diuretics, nitrates or calcium channel blockers) to rectify the situation before considering down-titration to the next lower study drug dose level.

Table 3-3 Safety monitoring criteria that must be met for dose uptitration

Parameter	Criteria
Blood pressure	SBP \geq 100 mmHg
Renal function	eGFR \geq 30 mL/min/1.73m ² and creatinine increase < 0.5 mg/dl from baseline
Serum potassium (or equivalent plasma potassium value)	K < 5.5 mmol/L (mEq/L)
AEs or conditions	No postural symptoms or any AEs that preclude up-titration according to the investigator's judgment

This is an event-driven trial, the study will continue until a total of at least 708 first confirmed primary triple composite endpoint events and at least 592 confirmed double composite events of first CV death or HF hospitalization (i.e., first secondary endpoint) have been achieved. Approximately 5,650 randomized post-AMI patients will be required to accrue the necessary number of confirmed endpoints. Once randomized, all patients will be followed until the total numbers of required confirmed endpoint events have been achieved and final follow-up has been performed.

It is anticipated that the total trial duration will be approximately 43 months, with a projected recruitment period of approximately 37 months, followed by approximately 4 months of follow-up after the last patient is enrolled to accrue the needed number of endpoints, the closeout period is expected to last an additional 1-2 months. The overall estimated mean follow-up time will be approximately 19 months for the study. Although these are the

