⁹ Local laboratories for serum potassium (or equivalent plasma potassium value), creatinine and eGFR are permitted to help guide dosing decisions prior to initial dosing and prior to each dose titration step until target dose is achieved (Visits 1, 101, 102, 103 and potentially 104; additional visits may be added as necessary until target dose level is achieved and/or during dose adjustments throughout the study). If screening (Visit 1) and randomization (Visit 101) occur on the same day, only one laboratory assessment will be required. If local laboratory assessments are not possible or it will take longer to receive results than through the central laboratory assessment, the central laboratory may be used instead.

■ [REDACTED]

¹¹ Serum and urine pregnancy tests will be performed locally. Serum pregnancy test (not required for post-menopausal women) to be performed at Visit 1. Urine pregnancy tests at visits 101 and annual (not required for post-menopausal women) or more frequently if required by local regulatory authorities. If screening (Visit 1) and randomization (Visit 101) occur on the same day, only serum pregnancy test will be required. If serum pregnancy test is positive during the screening and on a confirmatory serum β -hCG test, the patient must not be randomized and must be discontinued from the trial. After randomization (Visit 101) a positive urine pregnancy test requires immediate interruption of study drug and confirmation by serum pregnancy test. If positive upon confirmation test, the patient must interrupt study drug until after the pregnancy and lactation period.

■ [REDACTED]

■ [REDACTED]

¹⁴ For patient who at the end of the study are completing visit 199 on or before month 8 (visit 107 as per protocol schedule)

■ [REDACTED]

¹⁶ For patients who have not been titrated to dose level 3 by week 4, an unscheduled dose titration visit on or about week 6 should be considered to evaluate whether titration to the target dose, dose level 3, can be initiated.

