6.5.1 Physical examination

A complete physical examination will include the examination of general appearance, skin, neck (including thyroid), eyes, ears, nose, throat, lungs, heart, abdomen, back, lymph nodes, extremities, vascular and neurological. If indicated based on medical history and/or symptoms, rectal, external genitalia, breast, and pelvic exams will be performed.

A short physical exam will include the examination of general appearance and vital signs (BP [SBP and diastolic blood pressure (DBP)] and pulse). A short physical exam will be conducted at all visits starting from Visit 101 except where a complete physical examination is required (see [Table 6-1](#)).

Information from all physical examinations must be included in the eSource/source documentation at the study site. Significant findings that are present prior to signing informed consent must be included in the Medical History part of the CRF. Significant findings made after signing the informed consent which meet the definition of an AE must be recorded on the AE section of the CRF.

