2.7.1.1 Adverse events of special interest / grouping of AEs

Specific AEs of interest will be summarized separately in addition to the above analysis. These specific AEs of interest are: angioedema (AAC adjudicated), hyperkalemia, hypotension, renal impairment, cognitive impairment, hepatotoxicity, statin drug-drug interaction, anaphylaxis, hypersensitivity, malignancy, embryo-fetal toxicity/lethality and neonatal/infantile toxicity through exposure from breast milk. Besides providing the crude percentages, annualized exposure adjusted incidence rates will also be provided by treatment group.

The search paths for the related preferred terms (PTs), high level group term (HLGT), high level term (HLT), in Standard Medical Queries (SMQs), or NMQ in MedDRA for these risks are stored (or alternatively "summarized") in the latest version of LCZ696 Case Retrieval Strategy.

In addition to above standard analyses, for double blind phase, analysis for time-to-first selected AEs by treatment group will be performed using Kaplan-Meier estimate. The annualized exposure duration adjusted event rates will also be provided.

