2.7.4 Other safety data

2.7.4.1 Vital signs

Sitting systolic blood pressure (SBP), sitting diastolic blood pressure (DBP) and Sitting pulse pressure (PP) will be descriptively summarized by presenting summaries (n, mean, standard deviation, median, minimum, maximum) of actual value and change from baseline values for each scheduled assessment visit and treatment group.

The number and percentage of patients with clinically notable vital signs changes from baseline will be presented. Clinically notable vital sign results are provided in Table 2-8 below.

Table 2-8 Clinically notable changes in vital signs

Vital Sign (unit)	Clinically notable criteria
Weight (kg)	decrease > 7% from Baseline increase > 7% from Baseline
Sitting systolic blood pressure (mmHg)	<=90 and decrease from baseline >=20 >=180 and increase from baseline >=20
Sitting diastolic blood pressure (mmHg)	<=50 and decrease from baseline >=15 >=105 and increase from baseline >=15
Pulse (bpm)	<=50 and decrease from baseline >=15 >=120 and increase from baseline >=15

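### SAP 2.1.1 keeps blood pressure and pulse readings from unscheduled visits out of the clinically notable vital-signs table (Table 2-8), which can therefore understate notable low blood pressure

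*SAP*

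**What the plan says.** SAP 2.1.1 has a short paragraph on unscheduled visits. Its first sentence reads "Only for the analysis of safety laboratory evaluation will unscheduled measurements be taken into account". Its second says that efficacy evaluations will generally not use such measurements unless that is specified. Vital signs are not mentioned.

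SAP 2.7.4.1 describes two vital-sign outputs. The first is descriptive: actual values and "change from baseline values for each scheduled assessment visit and treatment group". The second is at patient level: "The number and percentage of patients with clinically notable vital signs changes from baseline will be presented". The thresholds are in Table 2-8; for low systolic pressure the criterion is "<=90 and decrease from baseline >=20". Nothing there says that unscheduled readings enter the second output.

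Protocol 3.1 and footnote 16 to Table 6-1 state that, for patients not at dose level 3 by week 4, "an unscheduled dose titration visit on or about week 6 should be considered". Protocol 3.1 also says: "Study drug dose level adjustments should be based on overall safety and tolerability with special focus on a) symptomatic hypotension". Under Protocol 6.5.1, "A short physical exam will be conducted at all visits starting from Visit 101", except where a complete examination is due; the short examination includes blood pressure and pulse.

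Hypotension is also an adverse event of special interest, and SAP 2.7.1.1 handles it separately: "Specific AEs of interest will be summarized separately in addition to the above analysis".

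**The concern.** A table of patients who ever crossed a threshold is meant to find the worst value. The SAP lets unscheduled laboratory values contribute to the notable laboratory table (Table 2-6) but shuts unscheduled blood pressure out of the matching vital-sign table, and gives no reason for the difference. The SAP's change history lists the unscheduled-visit rule and the vital-sign thresholds as additions in the same round of amendment, and nothing reconciles the two.

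The omitted readings are unlikely to be a random sample. Unscheduled visits are foreseen for patients whose titration has stalled, and low blood pressure is one of the named reasons for adjusting the dose level. SBP of at least 100 mmHg is also one of the up-titration criteria in Protocol Table 3-3.

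Safety and tolerability form a stated secondary objective, and SAP Table 1-2 lists vital signs next to laboratory assessments under it. Table 2-8 is the only planned hypotension output that rests on a measured threshold rather than on an investigator's decision to report an event.

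**Working it through.** There is no plan figure to reproduce. The check is a reading of the rules, followed by a look at what can be said about size.

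**1. Which readings reach Table 2-8.** The word *only* in SAP 2.1.1 limits unscheduled measurements to laboratory analyses. The clause that allows exceptions is attached to efficacy. SAP 2.7.4.1 specifies none. Followed as written, Table 2-8 uses scheduled readings alone.

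**2. Direction.** Let A be the patients with at least one notable scheduled reading and B those with at least one notable unscheduled reading. The plan counts |A|; the full count is |A ∪ B|. Since |A| ≤ |A ∪ B|, the table can understate and cannot overstate. The shortfall is the number of patients in B but not in A.

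**3. How easily the schedule could miss an episode.** The scheduled days in Table 6-1 are 1, 7, 14, 28, 61, 122, 243, 365 and so on. The gaps are 6, 7, 14, 33, 61, 121 and 122 days, and about 122 thereafter. If an episode lasts L days, starts at a random point and visits fall on their planned days, the chance that it covers a scheduled visit in a gap of G days is min(1, L/G). L is not in the documents, so three assumed values are shown.

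| Period (gap) | L = 7 | L = 14 | L = 28 |
|---|---|---|---|
| Days 1–14 (6, 7) | 100% | 100% | 100% |
| Days 14–28 (14) | 50% | 100% | 100% |
| Days 28–61 (33), contains week 6 | 7/33 = 21% | 14/33 = 42% | 28/33 = 85% |
| Days 61–122 (61) | 7/61 = 11% | 14/61 = 23% | 28/61 = 46% |
| After day 122 (about 122) | 7/122 = 6% | 14/122 = 11% | 28/122 = 23% |

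Coverage is good in the first month and thin after month 4. These are not shares of patients lost from the table: an episode missed by the schedule reaches set B only if the patient had an unscheduled visit and a reading was taken then.

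**4. Effect on the comparison between arms.** Let p1 and p2 be the true proportions of patients ever notable, and f1 and f2 the fractions of them notable only at unscheduled visits. The table shows p1(1 − f1) − p2(1 − f2). With assumed values p1 = 12% and p2 = 8%, a true difference of 4 points:
- f1 = f2 = 0.5 gives 6% − 4% = 2 points;
- f1 = 0.5, f2 = 0 gives 6% − 8% = −2 points;
- f1 = 0, f2 = 0.5 gives 12% − 4% = 8 points.

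So each arm's count is biased downward, but the bias in the difference can go either way. All four inputs are illustrative; the documents give none of them.

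**5. What the rule does not touch.** The hypotension event of special interest is found by a MedDRA search of reported adverse events (SAP 2.7.1.1). The double-blind summaries include all post-randomization events, on or off drug (SAP 2.7.1), and events may come to light between visits (Protocol 7.1). A rule about measurements does not restrict those records. No efficacy endpoint or alpha calculation uses vital signs.

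**The case against.** The strongest reply is that hypotension is already well covered. Reported hypotension is summarized with crude and exposure-adjusted rates. Events leading to down-titration, interruption or discontinuation are summarized (SAP 2.7.1), as are reasons for down-titration by dose level (SAP 2.4.1). A reader might infer from SAP 2.1.1 that the hypotension event of special interest is itself undercounted. The documents do not support that, for the reason in step 5. What remains is narrower: under Protocol 7.1 an abnormal result becomes an adverse event only if it causes signs or symptoms, is judged clinically significant or needs therapy. Table 2-8 is the check that does not depend on that judgement.

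A second reply is that scheduled-only readings give both arms the same opportunities to be measured, whereas unscheduled visits are prompted by symptoms or titration and may be more frequent in one arm. This is a real drawback of the change. It is a reason to show both versions, not to leave measured values at or below 90 mmHg out of a threshold-based safety table.

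A third is that the readings may not be in the database. Protocol 6.5.1 requires physical-examination findings, which include blood pressure and pulse, in source documents. The text on unscheduled visits and added visits during dose adjustment (Protocol 6.5.4 and Table 6-1, footnote 9) concerns potassium, creatinine and eGFR. Capture of blood pressure at unscheduled visits is likely but not proven, so it would be wrong to treat the data as certainly available.

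Finally, one could read the paragraph in SAP 2.1.1 as addressing only laboratory and efficacy data, with vital signs left open. The opening *only* makes that reading hard to sustain, and it would still leave Table 2-8 undefined.

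**Conclusion.** The point holds and is minor. As written, the plan excludes unscheduled blood pressure and pulse from Table 2-8, so the table can understate the number of patients with notable low blood pressure. The direction within each arm follows from the counting rule alone. The size is unknown, and so is the direction of any bias in the difference between arms.

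A reader might look at the visit spacing after month 4 and infer that about 89% of two-week episodes (1 − 14/122) could be documented only off-schedule. That goes too far: the two-week duration is an assumption, the spacing does not apply during the first four months, when most titration is planned, and an episode missed by the schedule need not produce an unscheduled reading at all.

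The conclusion rests on a literal reading of SAP 2.1.1 and on at least some unscheduled blood pressure readings being recorded in the database. It concerns one descriptive safety table.

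**What to change.** Amend SAP 2.1.1 and repeat the rule in SAP 2.7.4.1, along these lines: *Patient-level tables of clinically notable values, both laboratory (Table 2-6) and vital signs (Table 2-8), use all post-baseline readings in the database, scheduled and unscheduled. By-visit vital-sign summaries use scheduled visits only.* Add a scheduled-only version of Table 2-8 next to the main one, so that a reader can see how far the result depends on unequal numbers of readings.

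Before adopting this, confirm that blood pressure and pulse from unscheduled visits were entered in the clinical database. If they were not, say in a footnote to Table 2-8 that it rests on scheduled readings.

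The cost is a sentence in each of two sections, a change to one data-selection flag and one extra display. SAP section 1 allows for amendments finalized before database lock. Reported counts may rise in both arms. No visit, procedure or clinical rule changes.
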